| Study Objectives/Endpoints (RCT) | 
To determine if mobile application-guided education and exercise paired with accurate and sensitive activity monitoring, captured from consumer wearables for the entire episode of care can provide a viable (and potentially improved) alternative to current standard of care (SOC) for hip and knee arthroplasty.
 
Primary Endpoint: Non-inferior results between the current SOC and the mymobility platform for all-cause 30-day readmission rates.
 
Secondary endpoints include KOOS, JR. (Knee); HOOS, JR. (Hip), manipulation under anesthesia (knee), single leg stance test, timed up and go (TUG), satisfaction for those subjects who complete the mymobility program compared to those who complete traditional, standard of care education and rehabilitation.
 
Economic Analysis: Determine if subjects who complete the mymobility program incur less cost and fewer resources than subjects receiving traditional SOC. Potential data collection points include: number of PT visits, discharge disposition, ER visits, readmissions, reoperations, unscheduled surgeon visits, and time processing paperwork and approvals for the entire episode of care (30 days prior to surgery through 90 days post-op).
 |
| Indications/Target population | Inpatient and outpatient (including ASC) subjects indicated for unilateral, primary total or partial knee arthroplasty or total hip arthroplasty who meet the inclusion/exclusion criteria for study participation. |
| Inclusion/Exclusion criteria | 
Inclusion Criteria
 
 • Subject must be 18 years of age or older. • Subject qualifies for a primary, unilateral total or partial knee arthroplasty, based on a physical exam |

| | |

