| Informed Consent | X | | | | | |
| Inclusion/Exclusion Criteria | X | | | | | |
| Randomization (RCT only) | X | | | | | |
| Demographic & History Form* | X | | | | | |
| Physical Exam | X | | X | X | | |
| Procedure & Perioperative Information | | X | | | | |
| Other Device Documentation | | ◆ | | | | |
| Chart Review* | | | | X | | X |
| Patient Questionnaire #1 (EDC)* | ● | | | | | |
| Patient Questionnaire #2 (EDC)* | | | ● | | | |
| Patient Questionnaire #3 (EDC)* | | | | ● | | |
| EQ-5D-5L (EDC)* | ● | | ● | ● | ● | ● |
| KOOS, JR, HOOS, JR (via mymobility App). Control patients will complete in the EDC* | ● | | ● | ● | ● | ● |
| Adverse Event Form | | ◆ | ◆ | ◆ | ◆ | ◆ |
| Medical Event Log | | ◆ | ◆ | ◆ | ◆ | ◆ |
| Protocol Deviations* | ◆ | ◆ | ◆ | ◆ | ◆ | ◆ |
| Study Completion* | ◆ | ◆ | ◆ | ◆ | ◆ | ◆ |
| Time Documentation (Pilot Only) | X | X | X | X | | |

X Completed by Investigator or Designee

● Completed by subject (required)

◆ Completed by Investigator or Designee as applicable

* Forms that can be directly entered into the EDC system

V. Introduction and Purpose

Postoperative rehabilitation after total joint arthroplasty (TJA) has traditionally been initiated via discharge to a rehabilitation facility or through formal outpatient physical therapy (PT).¹ This has resulted in the cost of approximately \$648 million per year for PT after primary TJA, with up to 25% of these costs utilized on less common modalities.² As elective TJA patients have increased their mobility in the early postoperative period and hospital or ambulatory surgery center (ASC) length of stay has decreased over time, patient-initiated therapy has become an emerging alternative for postoperative recovery. Previous randomized controlled trials have demonstrated that monitored home exercises can have equivalent outcomes when compared to formal outpatient PT after TJA for both range of motion (ROM) and patient reported outcome measures (PROMs).³⁻⁸ However, there remains a substantial subgroup of patients (up to 20%) who may crossover to formal PT following patient-initiated therapy, highlighting a potential opportunity to provide an optimized home program that provides more effective simulated physical therapy in the postoperative TJA period.

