The Informed Consent process may be completed in-person or through an IRB/EC approved remote method. After completing the Informed Consent process, candidates who agree to enter the study must sign and date the IRB/EC approved ICF. The ICF must be signed and dated prior to onboarding. Study data will not be collected until the ICF has been signed and dated. If the candidate does not wish to participate (does not sign and date the ICF), data for that candidate will not be collected for this study.

A copy of the signed and dated ICF must be provided to the study subject. The original signed and dated ICF is to be filed in the subject's medical record, study subject binder, or regulatory binder.

D. Subject Enrollment

Once the ICF has been signed and dated by the subject, the subject will be considered enrolled in the study. A unique subject identification number (Subject ID) will be assigned to each participating subject.

This unique Subject ID number will be used throughout the study for identification. The subject will be considered an active study subject after receiving training in the appropriate use, participation and functionality of the mymobility platform and Apple Watch. In the event that the subject does not undergo knee or hip arthroplasty as outlined in the inclusion criteria, the subject will be considered a screen failure and a **Study Completion Form** will be used to document the subject's exit from the study.

E. Baseline/Preoperative Assessment

The following baseline/pre-operative data will be collected at the time of enrollment:

1. Inclusion/Exclusion Criteria
 - a. Randomization (RCT cohort only, recorded in EDC)
2. Demographics & History Form
3. Pre-op Physical Exam
 - a. Knee/Hip specific assessments including ROM

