 - Should an update of iOS or Watch OS be required, where possible, the update should be completed while the patient is at the site. In some situations, internet connectivity issues can cause significant delays with updating an OS. Under these circumstances the patient may complete the update at home. Additionally, Zimmer Biomet may approve a remote onboarding and watch pairing process for specific sites.
 - Turn on measurements of correct HealthKit data types.

- Review instructions on pairing of the Apple Watch, daily charging instructions, how to look at activity rings, set alerts, and other functionalities.
- iv. At this time, subjects with a compatible model of iPhone will also download the Apple Health and Fitness Recorder App to their iPhone. Following the download, the coordinator and subject will:
- Validate the correct data is being captured from the Apple Watch to the Apple Health and Fitness Recorder App.
- v. Subjects who do not already own an Apple Watch Series 3 or newer will receive one for use in the study.

2. Preoperative Time period (approximately 30 days before surgery)

- i. Subjects will begin to receive mymobility educational material through the App on their phones.
- ii. Collection of mymobility data will begin. This will include within-App questions that are answered by the subject, care plan adherence data and full time HealthKit data collected by the Apple Watch (steps, flights climbed, HR, stand hours) - transferred to the mymobility platform, except for times when the Apple Watch is being charged. At this time, applicable subjects will also have data collected by the Apple Health and Fitness Recorder App.
- iii. mymobility study subjects will follow the entire prescribed pathway of educational content, PROMs surveys, disposition questionnaires, and exercises until day of surgery in addition to their institution's standard of care preoperative procedures including education, classroom work and medical clearances.
- iv. Research coordinators or clinical staff may call subjects to remind them to complete all tasks as directed by mymobility and to confirm that they are charging and wearing the Apple Watch daily, not having problems using mymobility or the Apple Watch, etc. Study subjects will also be provided a direct phone number to the office research coordinator if they have questions regarding the mymobility App or Apple Watch functions.

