A medical event which is considered to be a normal post-operative symptomology or observation following any joint replacement surgery (e.g. joint pain, swelling, decreased range of motion, incisional pain) should not be classified as an adverse event unless it is considered to be more severe, of longer duration, is otherwise more pronounced than is typical, or is serious. Refer to **Section XIII** for the definition of a Serious Adverse Event. Events occurring after the index joint arthroplasty procedure discharge which are determined by the investigator to not be related to the joint arthroplasty procedure, device, use of the mymobility application or Apple Watch, should not be classified as adverse events, regardless of severity or seriousness.

Medical and adverse event collection will begin only after the patient has study surgery.

Specific instructions regarding Medical Events and Adverse Events:

- Readmission is defined as admittance to a hospital following discharge after the index joint surgery. This includes readmissions for observation as well as same day readmission/discharge. Prolonged hospitalization after the index joint surgery is not considered a readmission.
- If multiple medical events are all associated with the same medical issue, then it may be appropriate that only one adverse event is completed, rather than an adverse event for every medical event.
- Knee codes 30 to 60 are to be used for study joint knee events
- Hip codes 70 to 97 are to be used for study joint hip events
- Codes 01 to 29 are general or non-study joint events

*Normal: anticipated/expected in occurrence, severity, and seriousness. If the event does not meet all three criteria, this should be answered "No."

Reporting and Documentation of Adverse Events and Adverse Device Effects

Adverse Events and Adverse Device Effects will be documented on the Adverse Event Report form over the whole time of the investigation including information on the date of onset, treatment and resolution, as well as assessment of both the seriousness and the relationship to the study device. Further, the outcome of complications will be documented and any changes in outcome are to be updated during the course of the study. In case of early termination of the study, further follow-up of the patient shall proceed according to the hospital's standard procedure.

Reporting and Documentation of Serious Adverse Events, Serious Adverse Device Effects, and Device Deficiencies

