Serious Adverse Events and Serious Adverse Device Effects will be reported to the Sponsor as soon as possible. The incidence will be documented on the Adverse Event Report form over the whole time of the investigation including information on the date of onset, treatment and resolution, as well as assessment of both the seriousness and the relationship to the study device based on the evaluation of the investigator. The outcome of such complications will be documented and any changes in outcome will be updated during the course of the study. In case of early termination of the study, further follow-up of the study subject shall proceed according to the hospital's standard procedure.

Device Deficiencies (including the device, mymobility App, and Apple Watch) that did not lead to an adverse event but could have led to a medical occurrence if suitable actions had not been taken, if intervention had not been made, or if circumstances had been less fortunate shall be reported to the Sponsor as soon as possible.

The Investigator is responsible for reporting all SAEs, SADEs and Device Deficiencies that could have led to a SADE to the Ethics Committee or Institutional Review Board if required by national regulations or by the EC/IRB.

The Sponsor is responsible for determining the final classification of adverse events.

3. Revision

In the event that removal of one or more of the implanted devices used in the joint arthroplasty procedure is necessary, the Investigator will determine the best treatment and/or revision method for the subject.

Once the revision surgery has been completed, the Investigator or qualified Designee must complete an **Adverse Event Form**. Subjects who have tibial articulating surface exchanges may remain enrolled in the study. All other revisions will result in the subject being terminated from the study and a **Study Completion Form** must be completed.

4. Investigator Withdrawal

The Investigator can choose to withdraw a subject from the study if it is deemed to be in the subject's best interest or the subject does not consent to continue in the study after being informed of changes in the research that might affect them. The reason for the Investigator's withdrawal of the subject must be documented on the **Study Completion Form**.

5. Subject Withdrawal

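### Event forms open only after surgery, against the protocol's own whole-investigation rule, so a pre-operative App- or Watch-related harm has no planned adverse event record

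*Combined protocol and SAP*

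**What the plan says.** **Start of collection.** Section XII.D.2 sets an explicit start: "Medical and adverse event collection will begin only after the patient has study surgery". In the Section IV schedule, the pre-operative cell is empty for both the Adverse Event Form and the Medical Event Log. The pre-operative data list in Section X.E omits both forms, and the surgical and discharge list in Section X.G includes both.

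**The competing rule.** Later in Section XII.D.2: "Adverse Events and Adverse Device Effects will be documented on the Adverse Event Report form over the whole time of the investigation". The paragraph on serious adverse events and serious adverse device effects sets the same period. The synopsis says participation starts once informed consent is obtained.

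**Exposure.** Section XI.A.1 places App download and Watch pairing at a pre-operative visit up to 180 days before surgery. Section X.E suggests 14 to 30 days before. Under Section XI.A.2, App content and data collection begin about 30 days before surgery, and "mymobility study subjects will follow the entire prescribed pathway of educational content, PROMs surveys, disposition questionnaires, and exercises until day of surgery".

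**Exits.** Under Section X.D, if the arthroplasty does not take place, "the subject will be considered a screen failure and a" Study Completion Form documents the exit. That form has a pre-operative entry in Section IV. Sections XII.D.4 and XII.D.5 require it to state the reason for any investigator or subject withdrawal.

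**Economic window.** The synopsis plans resource use "for the entire episode of care (30 days prior to surgery through 90 days post-op"). The resource-utilization endpoint in Section VII defines the episode as the 90 days after surgery.

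**The concern.** The intervention under study is the App plus the Watch, not the implant. Its use begins before surgery, but the forms that capture harm are closed until surgery has happened. Section XV.A names wrist rash and pressure sores from the Watch as risks, and Section XII.D.2 counts events related to the App or Watch as adverse events. A wrist sore or a fall during an App exercise before surgery is therefore an adverse event by classification, at a time when collection has not begun.

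What is at stake is the completeness of the device safety record. Sites reading the two rules differently would report differently, so a count of device-related events would mix two collection windows. The contrast with device deficiencies is awkward as well. Deficiencies "that did not lead to an adverse event but could have led to a medical occurrence" are reportable with no stated start, while the rule for an actual harm depends on which sentence the site follows.

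There is a smaller economic consequence. The Medical Event Log is where new emergency and non-routine visits are entered, and it is closed during the 30 pre-operative days that the synopsis includes.

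**Working it through.** The plan states no figure on this point, so there is none to reproduce. The check compares the rules and then sizes the uncovered time.

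**Step 1: apply both rules to one case.** A subject is onboarded 30 days before surgery and develops a Watch-related sore 10 days later (a hypothetical case).
- Under the start rule and the schedule, no Adverse Event Form and no Medical Event Log entry are made.
- Under the whole-investigation rule, an adverse device effect is documented with onset, treatment, resolution, seriousness and relationship.
- Both cannot be followed. The schedule and the pre-operative data list side with the start rule, so a site would probably follow that one.

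**Step 2: look for another record of the same event.**
- Study Completion Form: open before surgery, but completed only if the subject leaves the study. It records the reason for exit. Nothing in the documents asks it for onset, seriousness or device relationship.
- Device deficiency reporting: limited to deficiencies that did not cause an adverse event, so actual harm falls outside it.
- Technical Support contact (Section XI.A.2): documents usage problems.
- Adherence and Watch data (Section XI.A.2): can show that use stopped, but not why.
- Chart review (Sections X.H and XII.D.7): looks for unreported medical and adverse events, with no stated look-back before surgery, and so inherits the start rule.

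A subject who is harmed, stops the device and stays in the study therefore has no form for the event or for the reason for stopping.

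**Step 3: size the uncovered time.** Formula: pre-operative days ÷ (pre-operative days + 365). Inputs are the 14 to 30 day suggestion (Section X.E), the 180-day limit (Section XI.A.1) and the 365-day follow-up.
- 14 ÷ (14 + 365) = 3.7%
- 30 ÷ (30 + 365) = 7.6%
- 180 ÷ (180 + 365) = 33.0%, the permitted maximum

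For the synopsis economic window, 30 ÷ (30 + 90) = 25% of the days fall while the Medical Event Log is closed. This is a share of time, not of cost or of visits.

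**Step 4: number of events.** The documents give no rate of pre-operative App or Watch harm, so a count cannot be derived. As an assumption only, a risk between 0.1% and 2% gives:
- 500 × 0.001 to 500 × 0.02 = 0.5 to 10 events in the RCT study group
- 10,000 × 0.001 to 10,000 × 0.02 = 10 to 200 events among all App users

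**Step 5: primary endpoint.** Section XII.D.2 defines a readmission as hospital admission after discharge from the index surgery. No readmission can occur in the closed period.

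**The case against.** The best reply is that the protocol does not exclude these harms. The whole-investigation wording, and the instruction to report serious events to the sponsor as soon as possible, have no surgical start. Read that way, a serious pre-operative device effect is reportable. That stands as far as it goes: the text conflicts, and it would be wrong to say that such harms can never be recorded. It does not settle which rule a site follows.

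A reader might also infer several stronger points that the documents do not support.
- *That device-caused withdrawals go unrecorded.* The Study Completion Form is open before surgery and must give the reason for withdrawal.
- *That a third of exposure is typically uncovered.* That figure applies only at the 180-day limit; the suggested visit is far closer to surgery.
- *That the ISO definitions in Section XIII and the classification list in Section XII.D.2 are further contradictions.* They say what counts as an event, not when collection starts.
- *That the pre-operative period is the only time device effects can be separated from surgical ones.* Watch wear continues to day 365 with the forms open, wrist lesions are distinguishable from joint surgery, and the RCT control arm is not given the App or Watch.
- *That the economic window cannot be filled.* The synopsis lists only potential data points, and some, such as readmission, can only follow surgery. Chart review captures emergency and non-standard visits, and a separate data program may supply visits at selected US sites (Section XII.B).

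The risk section also describes the intervention risk as negligible. That bears on how many events to expect, not on whether the two rules agree.

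**Conclusion.** The point holds as an internal contradiction with a practical gap. Under the start rule and the matching schedule, a pre-operative App- or Watch-related harm has no planned adverse event record, including in a subject who is onboarded and never operated on. A subject who stops the device and remains in the study also has no form for the reason.

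The uncovered share is modest at the suggested timing and large only at the permitted limit. The number of missed events is unknown, because every count rests on an assumed rate. The conclusion assumes that sites follow the explicit start sentence and the schedule over the general wording. If they did the reverse, the forms would be completed without a scheduled place for them.

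This is a safety-recording defect. The primary comparison, its sample size and the success rule are untouched. The economic part is a secondary inconsistency between the synopsis and Section VII.

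**What to change.** 1. Reconcile the start sentence in Section XII.D.2 with the whole-investigation wording there. Open the Adverse Event Form at App/Watch onboarding for non-randomised subjects, and at randomisation in both RCT arms so that the arms are observed over the same period.
2. Limit pre-operative reporting to device-related and serious events. State how this fits the existing rule in Section XII.D.2 that unrelated events after discharge are not adverse events, whatever their seriousness.
3. Add the pre-operative cell for the Adverse Event Form to the Section IV schedule, and add the form to the Section X.E list.
4. Choose one economic window for the synopsis and Section VII. If the 30 pre-operative days are kept, have the existing 3-month chart review look back over them.

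Opening the full Medical Event Log before surgery is not needed. It takes every new medical problem and non-routine visit, which would be a real burden across up to 10,500 subjects.

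The cost is protocol wording, one schedule cell, a few more forms and slightly more site work. No visits or subjects are added.
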